8.1.6. Rescue Medications

Hydrocodone/acetaminophen 5 mg/325 mg will be used as a rescue medication throughout the study. Rescue medication will be allowed prn during the Open Label Titration Phase and the Double-Blind Phase up to 30 mg/1950 mg/day of hydrocodone (5 mg)/acetaminophen (325 mg). However, the subject may not use, on average, more than one dose of rescue medication per day over the 7 days before randomization. Throughout the study, subjects will be instructed to record their pain intensity “at that moment” on the electronic diary prior to taking rescue medication.

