Reference Therapy, Dosage and Mode of Administration:

Placebo in the Double-Blind Phase:

Subjects randomized to Group 1 who are on 4 mg, 8 mg, or 12 mg CAM2038 q1w after the Titration Phase will receive 12 weekly SC CAM2038 placebo injections with matching or near-matching volumes to CAM2038 (0.64 mL) or CAM2038 q1w (0.16, 0.24 mL). Subjects randomized to Group 2 who are on 16 mg, 24 mg, or 32 mg CAM2038 q1w after the Titration Phase will receive 3 monthly SC CAM2038 placebo injections with matching or near-matching volumes to CAM2038

q4w (0.18, 0.27, or 0.36 mL).

Buprenex Test Dose in the Titration Phase

On Day 1 of the Titration Phase, subjects will receive a test dose consisting of an IM injection of Buprenex 0.30 mg (1.0 mL).

Rescue Medication in the Titration and Double-Blind Phases and Open Label Extension Phase:

Oral hydrocodone/acetaminophen, 5 mg/325 mg tablets, q4-6 h prn. The maximum daily dose is 15 mg/975 mg/day (three tablets) for subjects whose screening MED was 40-79 mg/day or 30 mg/1950 mg/day (six tablets) for subjects whose screening MED was \geq 80 mg/day. Subjects cannot take more than an average of one rescue tablet per day, in the week prior to randomization.

Criteria for Evaluation:

Primary Efficacy Endpoint:

The primary efficacy endpoint is the change from baseline in WAAPI and the primary timepoint will be Week 12 of the Double-Blind Phase.

Secondary Efficacy Endpoints:

The secondary efficacy endpoints are as follows:

- Change from baseline in the WAWPI scores at Week 12 of the Double-Blind Phase, based on an NRS-11.
- Percentage of subjects with a 30% or greater decrease in API from baseline to Week 12 of the Double-Blind Phase.
- Rescue medication usage (number of days used and total dose) during the Double-Blind Phase.
- Change from baseline to Week 12 of the Double-Blind Phase in EuroQoL Group 5-dimension 5-level self-report questionnaire (EQ-5D-5L) score.
- Change from baseline to Week 12 of the Double-Blind Phase in Work Productivity and Activity Impairment (WPAI) score.
- Time to loss of efficacy, defined as discontinuation of study drug for lack of efficacy.

Safety Endpoints:

- Occurrence of AEs throughout the study.
- Concomitant medication usage throughout the study.

Exploratory Endpoints:

- Change from baseline to Week 12 of the Double-Blind Phase in Clinical Global Impression of Improvement (CGI-I) scale (as assessed by the Investigator).

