4.3. Dose Rationale

The 4-mg weekly starting dose of CAM2038 q1w correspond to a daily morphine equivalent dose (MED) of 28.5 mg, using a more conservative conversion factor of 50 from BPN to morphine; thus, representing safe and suitable starting doses for subjects receiving ≥ 30 mg of morphine daily. In this study, subjects will be titrated to effect. An indicative a priori transition from daily morphine dose to weekly CAM2038 doses and monthly CAM2038 dose is given in Table 1 and Table 2 below, respectively:

Table 1: Conversion from Daily Morphine to Once Weekly CAM2038 Doses

Daily Morphine Dose (mg)	Daily Titration Morphine Dose, 75 % (mg)	Starting Once Weekly Dose
40 to <80	30 to 60	4 mg CAM2038
80 to 120	60 to 90	8 mg CAM2038
>120 to 160	90 to 120	16 mg CAM2038
>160 to 320	120 to 240	24 mg CAM2038
>320	>240	32 mg CAM2038

Table 2: Conversion from Once Weekly CAM2038 to Once Monthly CAM2038 Dose

Once Weekly Dose	Corresponding Once Monthly CAM2038 Dose
4 mg CAM2038	No corresponding monthly dose. Subjects will be kept on CAM2038 once weekly.
8 mg CAM2038	No corresponding monthly dose. Subjects will be kept on CAM2038 once weekly.
12 mg CAM2038	No corresponding monthly dose. Subjects will be kept on CAM2038 once weekly.
16 mg CAM2038	64 mg CAM2038
24 mg CAM2038	96 mg CAM2038
32 mg CAM2038	128 mg CAM2038

The MED will be calculated using the conversion factor for each opioid as described in [Table 3](#) (McPherson, 2009). Subjects taking methadone are allowed to screen; however, the down titration process should be discussed with the Medical Monitor.

Table 3: Opioid Conversion to Morphine Equivalent Dose

Equianalgesic Opioid Dosing			
Drug	Equianalgesic Doses (mg)		
	Parenteral	Oral	Sublingual
Sublingual Buprenorphine	NA	NA	1.5
Belbuca™ buccal film	NA	0.3	NA
Morphine	10	30	NA
Codeine	100	200	NA
Hydrocodone	NA	30	NA
Hydromorphone	1.5	7.5	NA
Meperidine	100	300	NA
Oxycodone	10*	20	NA
Oxymorphone	1	10	NA
Tramadol	100*	120	NA
		Morphine (PO) Equivalents	
*Fentanyl Patch 25mcg/hr (One patch q3 days)	NA	60 mg / d	NA
Butrans patch 10mcg/hr (One patch q week)	NA	80 mg / d	NA
*Methadone 20 mg PO qd	NA	40 mg / d	NA

* Contact Medical Monitor to discuss

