6.1.2. Open Label Titration Phase

Following the morphine IR treatment, subjects will enter the Titration Phase. On Day 1 of the Titration Phase, subjects will return to the clinic after a washout of at least a 12-hour from their last morphine IR dose, or 12-24 hours from their last BPN dose. Subjects who report a CLBP of ≥ 5 on the API scale and have a Clinical Opiate Withdrawal Scale (COWS) score of ≥ 5 , will receive a BPN test dose (Buprenex 0.30 mg IM injection) at the clinical site. After the Buprenex test dose, subjects will be assessed for any changes in QTcF (Fridericia's corrected QTc) and withdrawal. Subjects who tolerate the BPN test dose, do not show an increase >30 ms in QTcF within 1 hour after the test dose, and have a COWS score of <5 within 15 minutes after the test dose will receive the first dose of SC CAM2038 q1w within 4 hours (+30 minutes) after the test dose (4 mg CAM2038 for subjects whose screening MED was between 40 mg/day and 79 mg/day; and 8 mg CAM2038 for subjects whose screening MED was ≥ 80 mg/day).

During the first week of the Titration Phase, subjects who experience significant pain may, at the discretion of the investigator, receive an additional 4 mg (for subjects whose screening MED was 40-79 mg/day) or 8 mg CAM2038 (for subjects whose screening MED was ≥ 80 mg/day), on Day 3, 4 or 5. Dose adjustments will be made by increasing or decreasing the dose level of CAM2038 q1w at the scheduled weekly visits (doses of 4 mg, 8 mg, 12 mg, 16 mg, 24 mg, or 32 mg per week). Subjects who require doses >32 mg/week will be discontinued from the study.

Rescue medication, consisting of hydrocodone/acetaminophen 5 mg/325 mg every 4 to 6 hours (q4-6h), may be taken as needed (prn) up to 15 mg/975 mg/day (three tablets) for subjects whose screening opioid dose was between 40 and 79 mg/day MED or 30 mg/1950 mg/day (six tablets) for subjects whose screening opioid dose was ≥ 80 mg/day MED. The goal of the Titration Phase is to achieve a stable dose of CAM2038 q1w that produces analgesia, by the end of the 10-week period.

Eligible subjects will receive CAM2038 titrated to a dose that meets the following criteria (see also Section 7.4):

- Provides analgesia (i.e., 7-day mean API ≤ 4)
- The API is at least 2 points below the value at the start of CAM2038 titration
- The dose of CAM2038 is well-tolerated for 7 days before randomization (no adverse effects that require a change in study dosing or interruption)

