6.1.3. Double-Blind Phase

Subjects who are stabilized and responding to their CAM2038 q1w dose (4, 8, 12, 16, 24, or 32 mg/week) at the end of the Titration Phase and who fulfill the pre-defined randomization criteria will be randomized to one of two treatment groups in the 12-week Double-Blind Phase:

- Group 1: CAM2038 q1w or CAM2038 q4w SC injections
- Group 2: placebo q1w or placebo q4w SC injections

During the Double-Blind Phase, all subjects who are receiving 4, 8 or 12 mg CAM2038 q1w at the end of the Titration Phase will be randomized to continue their respective CAM2038 q1w dosing of 4 mg, 8 mg or 12 mg CAM2038, or to matching placebo q1w for a total treatment duration of 12 weeks. Subjects who are receiving 16 mg, 24 mg or 32 mg CAM2038 q1w at the end of the Titration Phase will be randomized to CAM2038 q4w (64 mg, 96 mg or 128 mg, respectively) or to matching placebo q4w for a total treatment duration of 12 weeks.

Figure 1: Overview of Study Design

¹ One booster is allowed on Day 3-5 after the first CAM2038, 4 or 8 mg injection. If booster is taken, the next dose on week 2 will be 8 or 12 mg, otherwise stay at 8 mg. Then titration is weekly up to 10 weeks. Final Study Visit is 1 week after the last CAM2038 q1w dose for q1w subjects and 4 weeks after the last q4w dose for q4w subjects. Follow-up is within 4 weeks after the Final study visit.

IR = immediate release; MED=morphine equivalent dose; q1w=once weekly; q4w=once monthly; R= randomization. There will be a Final Study Visit or Early Termination and one Follow-up Call.

Rescue medication, hydrocodone/acetaminophen 5 mg/325 mg q4-6h prn, will be allowed during the Double-Blind Phase (up to three tablets or 15 mg/975 mg/day for subjects whose MED at screening was between 40-79 mg/day and up to six tablets or 30 mg/1950 mg/day for subjects whose MED at screening was ≥80 mg/day). Whenever subjects take rescue medication, they must record their pain intensity “at that moment” prior to taking rescue medication in the electronic diary.

6.1.4. Follow-up Phase for Subjects Not Transitioning to the Open Label Safety Extension Phase

A Final Study Visit will take place 1 week after the last CAM2038/placebo q1w dose or 4 weeks after the last CAM2038/placebo q4w dose. At the Final Study Visit (or early termination), subjects will be transitioned back to standard care or to their treatment prior to study entry. Subjects will then be contacted

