8.1.4. Double-Blind Phase

Subjects who are receiving 4, 8 or 12 mg CAM2038 q1w at the end of the Titration Phase will be randomized to continue their respective 4 mg, 8 mg or 12 mg CAM2038 q1w dosing, or to corresponding placebo q1w for a total treatment duration of 12 weeks (12 injections in the Double-Blind Phase). Subjects who are receiving 16 mg, 24 mg or 32 mg CAM2038 q1w at the end of the Titration Phase will be randomized to CAM2038 q4w (64 mg, 96 mg or 128 mg, respectively) or to corresponding placebo q4w for a total treatment duration of 12 weeks (3 injections in the Double-Blind Phase).

The dose conversions between CAM2038 q1w and CAM2038 q4w are shown below.

- 4 mg CAM2038 q1w = 4 mg CAM2038 q1w or placebo q1w
- 8 mg CAM2038 q1w = 8 mg CAM2038 q1w or placebo q1w
- 12 mg CAM2038 q1w = 12 mg CAM2038 q1w or placebo q1w
- 16 mg CAM2038 q1w = 64 mg CAM2038 q4w or placebo q4w
- 24 mg CAM2038 q1w = 96 mg CAM2038 q4w or placebo q4w
- 32 mg CAM2038 q1w = 128 mg CAM2038 q4w or placebo q4w

CAM2038/placebo q1w must not be administered into a previously injected site for at least 4 weeks. CAM2038/placebo q4w must not be administered in a site previously injected with CAM2038/placebo q4w or with CAM2038/placebo q1w.

During the entire Double-Blind Phase, subjects will be instructed to record their pain intensity ratings before taking rescue medication. Rescue medication will consist of hydrocodone/acetaminophen 5 mg/325 mg tablets, q4-6h prn, not to exceed a total of 6 tablets or a total dosage of hydrocodone/acetaminophen 30 mg/1950 mg/day for subjects whose screening opioid dose was ≥ 80 mg/day. For subjects whose screening opioid dose was between 40 and 79 mg/day MED, the maximum allowable rescue medication will be 15 mg/975 mg/day (three tablets). This dosage limit will provide analgesic rescue medication at a maximum dose to prevent liver toxicity.

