In addition, at any time during the Double-Blind Phase, if the subject requires rescue medication above the maximum allowable (hydrocodone/acetaminophen 30 mg/1950 mg/day (six tablets) for subjects whose screening MED was ≥ 80 mg/day; or 15mg/975 mg/day (three tablets) for subjects whose screening MED was between 40 and 79 mg/day), the subject should be asked if they want to continue with the maximum dose of rescue medication or would like to withdraw from the study. If circumstances surrounding discontinuation or withdrawal are unclear, the Medical Monitor should be consulted. If the subject decides to withdraw, the subject should have a final on-treatment visit and then have procedures and assessments completed for any remaining study visits, as specified in the protocol.

Telephone or other contacts made by the site are allowed throughout the course of the study. Subjects should return to the study center according to the schedule specified in this protocol.

One week after the last dose of CAM2038/placebo q1w or 4 weeks after the last dose of CAM2038/placebo q4w, the subjects will attend a Final Study Visit. At the Final Study Visit (or early termination), subjects will be transitioned back to standard care or their treatment prior to study entry. Within 4 weeks after the Final Study Visit, subjects will be contacted by phone to assess AEs and review concomitant medications.

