8.4. Selection of Dose

The study will include the following doses based on each subject's individual analgesia needs and tolerability:

- CAM2038 q1w 6.25 mg/mL: 4 mg (BPN base); 0.64 mL SC injection
- CAM2038 q1w 50 mg/mL: 8 mg, 12 mg, 16 mg, 24 mg, and 32 mg (BPN base); 0.16, 0.24, 0.32, 0.48, and 0.64 mL SC injection
- CAM2038 q4w, 356 mg/mL: 64 mg, 96 mg, and 128 mg (BPN base); 0.18, 0.27, and 0.36 mL SC injection.

Dose adjustments will be allowed during the Open Label Titration Phase only.

Rescue medication is oral hydrocodone/acetaminophen, 5 mg/325 mg tablets, q4-6 h prn. The maximum daily dose is 30 mg/1950 mg/day. Subjects cannot take more than one rescue tablet per day, on average, in the week prior to randomization.

On Day 1 of the Titration Phase, subjects will receive a test dose consisting of a single IM injection of 0.30 mg (1.0 mL) Buprenex and will be assessed for any changes in QTcF or withdrawal prior to any administration of CAM2038.

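### Protocol sections 8.1.6 and 8.4 give every subject the six-tablet rescue maximum and omit the three-tablet limit for screening MED 40-79 mg/day

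*Protocol*

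**What the plan says.** Two sections of the protocol give one daily rescue maximum for everyone. Section 8.1.6 allows rescue as needed in the open-label titration and double-blind phases "up to 30 mg/1950 mg/day of hydrocodone (5 mg)/acetaminophen (325 mg". Section 8.4 states: "The maximum daily dose is 30 mg/1950 mg/day". Neither mentions screening MED, and neither refers the reader to another section for a lower limit.

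Elsewhere the maximum depends on screening MED:

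- Synopsis, rescue medication entry (titration, double-blind and extension phases): "The maximum daily dose is 15 mg/975 mg/day (three tablets) for subjects whose screening MED was 40-79 mg/day", with six tablets for 80 mg/day or more. The synopsis methodology text repeats the split for titration and again for the double-blind phase.
- Section 6.1.2 (titration): "up to 15 mg/975 mg/day (three tablets) for subjects whose screening opioid dose was between 40 and 79 mg/day MED".
- Section 6.1.3 (double-blind): "up to three tablets or 15 mg/975 mg/day for subjects whose MED at screening was between 40-79 mg/day".
- Section 8.1.4 (double-blind): for the 40-79 mg/day group "the maximum allowable rescue medication will be 15 mg/975 mg/day (three tablets"; and again, in the rule for subjects who need more than the maximum, "15mg/975 mg/day (three tablets) for subjects whose screening MED was between 40 and 79 mg/day".

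**The concern.** Sections 8.1.6 and 8.4 sit in the treatment chapter, and 8.1.6 is the section headed for rescue medication. A site that looks up the limit there finds six tablets a day and no sign that a lower limit applies to some subjects. For a subject with screening MED 40-79 mg/day that is the wrong limit.

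What is at stake is opioid exposure. The extra rescue would be taken with depot buprenorphine, and section 8.7 warns that other CNS depressants used with it may cause respiratory and CNS depression. The acetaminophen excess matters less, because the protocol accepts 1950 mg/day in the higher-MED group. A secondary effect falls on diversion monitoring: section 8.2.5 gives excessive rescue use as an example of suspected diversion, and two different maxima make that hard to apply evenly across sites.

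**Working it through.** **Inputs.** One tablet is hydrocodone 5 mg/acetaminophen 325 mg (section 8.1.6). The limits are those listed above. For opioid equivalence, section 4.3 states that "The MED will be calculated using the conversion factor for each opioid as described in" Table 3, where 30 mg oral hydrocodone corresponds to 30 mg oral morphine, so 1 mg of hydrocodone counts as 1 mg of MED.

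**Step 1: reproduce the stated limits.**

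- 3 tablets: 3 × 5 = 15 mg and 3 × 325 = 975 mg.
- 6 tablets: 6 × 5 = 30 mg and 6 × 325 = 1950 mg.

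Both reproduce exactly. The single maximum in 8.1.6 and 8.4 is therefore the six-tablet limit that the other sections reserve for screening MED of 80 mg/day or more.

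**Step 2: set the sections side by side.**

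| Protocol location | Phase | Limit, MED 40-79 | Limit, MED 80 or more |
|---|---|---|---|
| Synopsis, rescue entry | Titration, double-blind, extension | 3 tablets | 6 tablets |
| Section 6.1.2 | Titration | 3 tablets | 6 tablets |
| Section 6.1.3 | Double-blind | 3 tablets | 6 tablets |
| Section 8.1.4 | Double-blind | 3 tablets | 6 tablets |
| Section 8.1.6 | Titration, double-blind | 6 tablets (no MED condition) | 6 tablets |
| Section 8.4 | None stated | 6 tablets (no MED condition) | 6 tablets |

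Section 8.4 closely tracks the synopsis rescue entry, including the limit of one tablet a day on average in the week before randomization. The MED split is what has dropped out.

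**Step 3: size of the discrepancy.** For MED 40-79 mg/day: 30/15 = 2 for hydrocodone and 1950/975 = 2 for acetaminophen.

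**Step 4: scale against prior opioid dose (illustration).** Maximum daily rescue hydrocodone as a share of screening MED:

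- Split limits, MED 40-79: from 15/79 = 19.0% to 15/40 = 37.5%.
- Split limits, MED 80 or more: at most 30/80 = 37.5%.
- Single limit applied to MED 40-79: from 30/79 = 38.0% to 30/40 = 75.0%.

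The split keeps the maximum at or below 37.5% in both groups. The single limit puts it above that level throughout the lower group.

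**Step 5: where in section 8 a site could find the right limit.** For the double-blind phase, section 8.1.4 gives both limits and says what to do when a subject needs more. For titration, section 8.1.3 gives no rescue limit, and Table 5 lists rescue dispensing without one. The rule in 8.1.4 for exceeding the maximum covers only the double-blind phase. So within section 8 the only titration maximum is the six-tablet figure in 8.1.6, repeated without a phase in 8.4; the correct one has to be found in the synopsis or section 6.1.2.

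**Step 6: effect on the analysis.** SAP section 9.5.7 derives only the number of days with rescue use from the electronic diaries, because total dose was judged unreliable. A difference in tablets per day does not enter that endpoint directly.

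**The case against.** The strongest reply is that 8.1.6 and 8.4 omit a qualifier without denying it. Thirty milligrams is the true study-wide ceiling, and a general statement can be read as subject to the specific lower limit given repeatedly elsewhere. Section 8.1.4 states the split shortly before 8.1.6, and section 8.1.7, immediately after, again refers to rescue requirements by MED group. Section 8.4 lists the doses available in the study and is not a dispensing instruction. Harm would require a site to rely on 8.1.6 or 8.4 alone and a lower-MED subject to want more than three tablets; randomized subjects have averaged no more than one a day in the preceding week.

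Much of this stands. The intended rule is recoverable, the point is weaker for 8.4 than for 8.1.6, and nothing shows that any site was misled. The share-of-MED percentages measure against a ceiling the protocol never set: the rationale in 8.1.4 is liver toxicity, and at a MED of 79 mg/day the difference between 38.0% and 37.5% is trivial.

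The reply does not cure the text. Section 8.1.6 names the phases it covers and gives them one limit. The nearby statement in 8.1.4 concerns the double-blind phase only, and the reference in 8.1.7 concerns the extension. The one-tablet average is a condition for randomization, so it does not restrain rescue use earlier in titration.

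**Conclusion.** The concern holds. Sections 8.1.6 and 8.4 state an operational opioid dose limit that is wrong for subjects with screening MED 40-79 mg/day: six tablets a day where three are intended, a two-fold difference in both components. The exposure is greatest in titration, where section 8 offers no correct figure.

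This rests on taking the two-limit rule as the intended one, which its repetition in the synopsis and in sections 6.1.2, 6.1.3 and 8.1.4 supports. The practical frequency is unknown, since the documents give neither the size of the lower-MED group nor how often its members would take more than three tablets. It is an internal inconsistency in dosing text and no criticism of the split rule itself. No bias in the efficacy results is claimed.

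**What to change.** In sections 8.1.6 and 8.4, replace the single maximum with the two limits from the synopsis rescue entry: three tablets (15 mg/975 mg) a day for screening MED 40-79 mg/day, and six tablets (30 mg/1950 mg) a day for screening MED of 80 mg/day or more. The cost is one clause in each of two protocol sections. Design, sample size and analysis are unaffected.

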8.1.7. Open Label Safety Extension

Once the required number of subjects for the Double-Blind phase of the trial has been recruited (approximately 340), enrollment for the Double-Blind Phase will be closed and remaining subjects with CLBP will be offered the opportunity to proceed directly to the Open Label Safety Extension Phase without having to participate in the Double-Blind Phase. However, to be eligible to proceed to the Open Label Safety Extension Phase, subjects must meet the following criteria:

- The analgesic dose of CAM2038 is well-tolerated for 7 days before entry into open label study (no adverse effects that require a change in study dosing or interruption)

The opening of recruitment for subjects with CLBP for the safety extension only after enrollment for the randomized Double-Blind Phase of the study is complete, is to ensure that eligible subjects with CLBP are enrolled into the pivotal randomized Double-blind phase first. However, other subjects with chronic pain requiring daily treatment with opioids, who do not qualify for the randomized Double-Blind Phase of the study but are eligible for the safety extension phase may be enrolled directly into the safety extension phase (so called de novo subjects). These subjects will not be required to wait for recruitment for the randomized Double-Blind Phase to be completed prior to enrolling into the safety extension. The purpose of the safety extension is to ensure that sufficient data is obtained, to provide at least 52 weeks of exposure safety information in at least 100 subjects. These long long-term safety data are required to support the clinical development of CAM2038 for the indication of chronic pain requiring daily treatment with opioids.

De novo subjects proceeding directly to the open label extension, will undergo the same screening procedures, down titration, morphine IR, Buprenex test dose, and CAM2038 up-titration similar to the requirement for subjects enrolling into the randomized Double-Blind Phase of the study. The CAM2038 dosing titration and rescue medication requirements for the safety extension for subjects whose opioid doses at screening are > 80 mg/day MED, and 40-79 mg/day MED, respectively, shall be the same as described for the subjects participating in the Double-Blind Phase.

Subjects in the safety extension will return to the study clinic for their regular weekly or monthly CAM2038 injections until the end of the study.

Starting at the fourth monthly safety extension visit, PK sampling for CAM2038 steady state PK will be performed in subjects who have provided additional consent for the PK sampling. PK sample can be done at any visit timepoint after the subject has stabilized but no later than 4 week prior to EOT visit. Effort will be made to ensure that a sufficient number of subjects are included to cover the range of CAM2038 doses in the safety extension phase.

Blood samples will be collected prior to administration (within 45 minutes); and at approximately 2 hours, 6 hours, 24 hours, 72 hours, 168 hours, 336 hours, and 672 hours to measure plasma levels of BPN and norBPN for subjects receiving both CAM2038 q1w and CAM2038 q4w treatments. Actual dates and times of dosing of IMP during the safety extension phase as well as blood sampling for PK measurement will be recorded.

